## 5.d Classification of Events

### i Relationship

The definitions for the terms listed that should be used are those provided by the Department of Health and Human Services' Office for Human Research Protections (OHRP). A copy of this guidance can be found on OHRP's website: <http://www.hhs.gov/ohrp/policy/advevntguid.html>

### ii Severity

The descriptions and grading scales found in the revised NCI Common Terminology Criteria for Adverse Events (CTCAE) version 4.0 will be utilized for all toxicity reporting. A copy of the CTCAE version 4.0 can be downloaded from the CTEP website: <http://evs.nci.nih.gov/ftp1/CTCAE/About.html>

### iii Expectedness

Unanticipated problems are defined as:

- Unexpected (in terms of nature, severity, or frequency) given (a) the research procedures that are described in the protocol-related documents, such as the IRB-approved research protocol and informed consent document; and (b) the characteristics of the subject population being studied.
- Related or possibly related to participation in the research ("possibly related" means there is a reasonable possibility that the incident, experience, or outcome may have been caused by the procedures involved in the research).
- Suggests that the research places subjects or others at a greater risk of harm (including physical, psychological, economic, or social harm) than was previously known or recognized.

## 5.e Data Collection Procedures for Adverse Events

Patients will be interviewed about adverse events during scheduled follow-up. Laboratory studies will be reviewed at each visit.

## 5.f Reporting Procedures

The PI is required to promptly notify the IRB of the following events:

- Any unanticipated problems involving risks to participants or others which occur at any WU, BJH or SLCH institution, or that impacts participants or the conduct of the study.
- Noncompliance with federal regulations or the requirements or determinations of the IRB.
- Receipt of new information that may impact the willingness of participants to participate or continue participation in the research study.

## 5.g Adverse Event Reporting Period

These events must be reported to the IRB within 10 working days of the occurrence of the event or notification to the PI of the event. The death of a research participant that qualifies as a reportable event should be reported within 1 working day of the occurrence of the event or notification to the PI of the event.

### **5.h Post-study Adverse Event**

Post-study adverse events will be identified through routine follow-up of these patients with chronic diseases by their treating physicians.

### **F6 Study Outcome Measurements and Ascertainment**

1. Inflammatory lesions will be based on optical coherence tomography (OCT) and slit lamp exam by the treating ophthalmologist
2. Anterior chamber cell will be measured according to Standardization of Uveitis Nomenclature (SUN) Working Group criteria; scores range from 0 to 4+, with higher scores indicating more cells visible in the anterior chamber and greater severity of uveitis (18)
3. Vitreous haze will be measured according to National Eye Institute [NEI] criteria adapted by the SUN Working Group; scores range from 0 to 4+, with higher scores indicating greater severity of uveitis (19)
4. Visual acuity will be measured by Early Treatment Diabetic Retinopathy Study chart
5. Cystoid Macular Edema will be measured by Optovue OCT
6. Angiography will be performed with the Optovue OCT
7. Intraocular Pressure will be measured with a Goldmann applanation tonometer by the treating ophthalmologist
8. Cataract formation will be assessed on physical exam by the treating ophthalmologist

## **G Statistical Plan**

### **G1 Sample Size Determination and Power**

This is a pilot study evaluating the off-label use of tofacitinib for the treatment of non-infectious inflammatory eye disease. A maximum of 5 patients with uveitis will be enrolled. All analyses will be descriptive in nature.

### **G2 Interim Monitoring and Early Stopping**

The study Principal Investigator will monitor for serious toxicities on an ongoing basis. Once the Principal Investigator becomes aware of an adverse event, he will report the adverse event to the HRPO according to institutional guidelines. The trial will be stopped early if the number of serious toxicities exceed the expected rate (15). For example, the trial will be stopped if there are 3 or more cases of shingles while on tofacitinib therapy.

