## **2.e Risks and Benefits**

As with other immunosuppressive treatments to control autoimmune diseases, the patients will be at increased risk of infection (20%). Other risks include nasopharyngitis (3% to 14%), hypertension (2%), headache (4% to 9%), rash (6%), acne vulgaris ( $\geq 2\%$ ), increased serum cholesterol (5% to 9%), diarrhea (4% to 5%), gastroenteritis (4%), nausea (4%), urinary tract infection (2%), anemia (4%), herpes zoster infection (5%; including disseminated cutaneous, meningoencephalitis, ophthalmologic), increased creatine phosphokinase (3% to 7%), increased serum creatinine ( $< 2\%$ ), upper respiratory tract infection (4% to 6%), and fever ( $\geq 2\%$ ).

Lymphoma and other malignancies have been reported in patients receiving tofacitinib

Tuberculosis (pulmonary or extrapulmonary) has been reported in patients receiving tofacitinib. Standard laboratory screening is performed in all patients to assess for latent / chronic infection, such as TB.

There is a risk associated with lack of efficacy. In the case of a treatment failure based on the primary outcome criteria, tofacitinib will be discontinued and the patient will be switched to an alternative steroid-sparing therapy at the discretion of the patient's treating physician.

Potential benefits include improved control of the ocular inflammatory disease, reduced corticosteroid usage, reduced intraocular pressure, improved visual acuity, and prevention of permanent vision loss. The participants may also derive benefit from contributing to medical research.

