## **2.i Cessation of tofacitinib therapy**

### **i Indications for cessation of tofacitinib therapy**

- Laboratory abnormalities:
  - New elevation of ALT or AST > 3x upper limit of normal
  - New leukopenia with ANC < 1.5
  - New anemia with hemoglobin <7 g/dl or a decrease of > 3g/dl
  - New renal failure that would preclude the safe administration of tofacitinib
    - Patients may restart tofacitinib after recovery of renal function
- Clinical events:
  - Shingles or opportunistic infection:
    - Patients that develop an opportunistic infection or shingles may opt to (1) withdraw from the study or (2) hold tofacitinib while undergoing treatment with antivirals or antibiotics
  - Hospitalization due to tofacitinib
    - Any patient hospitalized secondary to treatment with tofacitinib as determined by a rheumatology research clinician.
  - Infection with tuberculosis:
    - Patients that develop active mycobacterium tuberculosis. All patients will have undergone screening with a PPD or interferon gamma release assay to rule out TB at the beginning of the study.
  - Treatment failure after week 8

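### The only numeric stopping boundary, 3 shingles cases among at most 5 patients, is looser than the rule it illustrates: against the only printed zoster rate, 2 of 5 already exceeds expectation

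*Combined protocol and SAP*

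**What the plan says.** Section G2 of the combined protocol and SAP gives a general rule: "The trial will be stopped early if the number of serious toxicities exceed the expected rate (15", where 15 is a reference number. It prints no rate, no period and no allowance for chance. One number follows, introduced as an example: "the trial will be stopped if there are 3 or more cases of shingles while on tofacitinib therapy". G2 also has the principal investigator watch for serious toxicities throughout and report adverse events to the HRPO under institutional guidelines.

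Other sections bear on this:

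- Section G1: "A maximum of 5 patients with uveitis will be enrolled". Section E3, 3.c puts everyone in one group.
- Section 2.e lists "herpes zoster infection (5%; including disseminated cutaneous, meningoencephalitis, ophthalmologic" among the risks, without a source or time base. It is the only zoster rate in the document.
- Section 2.i deals with the individual case: "Patients that develop an opportunistic infection or shingles may opt to (1) withdraw from the study or (2) hold tofacitinib" during treatment of the infection.
- Section E1 sets 24 weeks of study, with a possible further year for responders.
- Section I1 has the investigators review safety data weekly. Section F5, 5.b names the investigator as the only medical monitor.
- Sections 5.d(iii) to 5.g send "Any unanticipated problems involving risks to participants or others" to the IRB. The definition includes research-related problems that are "Unexpected (in terms of nature, severity, or frequency", and on timing 5.g says "These events must be reported to the IRB within 10 working days".

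**The concern.** A rule and its worked example should give the same answer on the same data. Here the rule compares a count with an expected rate, while the example waits until more than half of the largest possible sample is affected. G2 holds the only numeric trial-level safety boundary in the plan, and no independent monitor is there to interpret it. Whoever applies it will probably use the number, and the number says nothing about 2 cases.

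What is at stake is continued dosing of the other three patients after two of five have had shingles. All patients start a 60 mg prednisone taper and some keep a conventional immunosuppressant (section 3.f). The zoster forms listed in section 2.e include disseminated, meningoencephalitic and ophthalmologic disease.

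**Working it through.** **Inputs.** n = 5 (G1); example count 3 (G2); zoster rate 5% (2.e), assumed to stand in for the unprinted rate in reference 15; one case per patient; patients independent.

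**The plan's figure.** 3/5 = 60%, which is 12 times 5%. The plan gives no derivation of 3, so there is nothing further to reproduce.

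**Literal reading of the rule.** Expected cases are 5 × 0.05 = 0.25. One of 5 is 20% and two of 5 is 40%, and both exceed 5%. Three is the first exceeding count only if the expected rate is at least 40% and below 60%.

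**Allowing for chance.** With X binomial(5, p), at p = 0.05:

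- P(X ≥ 1) = 1 − 0.95^5 = 0.226
- P(X ≥ 2) = 0.226 − 5(0.05)(0.95^4) = 0.0226
- P(X ≥ 3) = 0.0012

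A stop at 1 case would trigger falsely 22.6% of the time, which is too often to be useful. Two is the smallest count with a one-sided false-trigger chance under 5%, or under 2.5%.

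**Chance that each count triggers, by true rate.** The rates above 5% are scenarios; the document does not predict them.

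| True rate | Count of 3 | Count of 2 |
|---|---|---|
| 5% | 0.1% | 2.3% |
| 10% | 0.9% | 8.1% |
| 20% | 5.8% | 26.3% |
| 30% | 16.3% | 47.2% |
| 40% | 31.7% | 66.3% |

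**Range for the unknown expected rate.** Solving P(X ≥ 2) = 0.05 gives p = 7.6%, and P(X ≥ 3) = 0.05 gives p = 18.9%. With a 5% one-sided limit (chosen here; the plan states none), 2 is acceptable up to 7.6%, which is 1.5 times the printed rate. From 7.6% to 18.9%, 3 is the smallest acceptable count. With a 1% limit, 3 is the smallest acceptable count from 3.3% to 10.6%, which includes 5%.

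**Time base.** If 5% is per year, a constant hazard gives 1 − 0.95^(24/52) = 2.3% over 24 weeks, and P(X ≥ 2) falls to 0.5%. Two cases would then be further from expectation.

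**The case against.** The strongest reply is that the example only says when the trial must stop; it does not say that the trial continues at 2. A reader might infer that the rule and the example contradict each other, or that the plan requires dosing to go on after two cases. The wording supports neither, because the general rule still applies at 2. The supported claim is narrower: the printed number is looser than the rule.

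A second objection is that 5% is not the rule's comparator. It is undated and uncited, and reference 15 may give something else. That stands, which is why the rate must be printed first. The prednisone taper or a retained conventional agent could also put the expected rate above 7.6%, and then 3 would be defensible as the only count.

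Third, the choice of 2 depends on the false-trigger limit. This stands too: at a 1% limit, 3 is right for a 5% rate, and a strict limit is reasonable where triggering ends the trial. It is less compelling for a pause that can be reversed.

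Fourth, other safeguards exist. HRPO reporting under G2, weekly review, withdrawal or drug hold for each affected patient, and the IRB route would probably make two cases visible outside the team. They reduce the harm, but none sets a trial-level count.

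A reader might also infer a large further risk to the other three patients. The formula 1 − (1 − p)^3 gives 14.3% at 5% and 48.8% at 20%, but these are upper values, since they assume a full period of risk remains. With half the exposure left they are 7.4% and 28.4%. The point does not rest on them.

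**Conclusion.** The point holds in its limited form. The only numeric boundary is 60% of the sample, while the rule it illustrates is exceeded at 2 of 5 when 5% is the expected rate (0.25 cases expected, P = 2.3%). Read literally, 2 of 5 exceeds any expected rate below 40%. An investigator working to the printed number would continue at 2 of 5, and at a true rate of 30% would fail to stop the trial about 84% of the time.

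The conclusion assumes 5% as a stand-in, one case per patient, and a 5% one-sided limit for preferring 2 to 3. Confidence is medium because the reference rate cannot be seen. The change is worth making, but the existing safeguards mean that patients are not left unprotected without it.

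**What to change.** In section G2:

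1. Print the expected shingles rate from reference 15 and the period it covers.
2. Add: *if 2 patients develop shingles within the 24-week period, enrolment and dosing are paused pending IRB review; the trial stops at 3.* Counting patients also settles whether repeat episodes in one person count.
3. If the expected 24-week rate exceeds about 7.6%, keep 3 as the only count and say why.

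The cost is one or two sentences, plus a 2.3% chance of a false pause at a 5% rate, against 0.1% for a count of 3. A pause interrupts treatment for patients whose steroids are being tapered, though section 2.b makes rescue corticosteroids available. It is also milder than the stop that the general rule would imply at 2, which suits an expected rate that is still uncertain; the IRB review can turn it into a stop.

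The pause is limited to 24 weeks because the extension lengthens exposure. If 2 or 3 of the 5 patients extend (assumed from the 40–60% failure expected in G3) and 5% is per 24 weeks, a count of 2 run through 76 weeks would trigger falsely 6.4% to 9.4% of the time, against 0.5% to 1.0% for a count of 3.

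The change does not make the rule sensitive. A count of 2 still misses 91.9% of the time at a true rate of 10% and 52.8% at 30%, a limit set by five patients.

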### **G3 Analysis Plan**

All analysis will be descriptive. We expect 40-60% of patients to meet the primary endpoint in each arm similar to adalimumab in the treatment of noninfectious uveitis. This is in contrast to the placebo arm, which had a treatment failure rate of 80% at 24 weeks (12).

Patients will be analyzed by intent to treat when all 5 patients in a treatment arm have either completed 6 months of therapy or discontinued therapy due to study withdrawal or indications for treatment cessation.

#### ***G4 Statistical Methods***

All analysis will be descriptive. This study is not powered to draw statistical conclusions.

#### ***G5 Missing Outcome Data***

Patients with missing outcome data in the primary endpoints will be censored for the initial analysis for efficacy.

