## **C Study Objectives**

### **C1 Primary Aim**

The primary endpoint will be treatment failure at week 24:

Treatment failure will be defined as

- Before or at week 8 (any one of the following criteria)
  - new inflammatory lesions relative to baseline
  - anterior chamber cell or vitreous haze > 0.5+ on SUN scale
  - worsening of visual acuity by two or more rows on ETDRS (Early Treatment of Diabetic Retinopathy Study) chart
- After week 8 (any one of the following criteria)
  - new inflammatory lesions relative to baseline
  - 2-step increase in anterior chamber cell or vitreous haze
  - worsening of visual acuity by two or more rows on ETDRS chart

Grade '0' will denote zero cells present per high power field or no vitreous haze and a change of full number grade will represent a "step change" (e.g. a change from grade 1 to 0 is considered a 1-step change).

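### On its natural reading, G5 turns the intent-to-treat failure rate promised in G3 into an observed-case rate, and G3's trigger can leave a week-24 status unknown (minor)

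*Combined protocol and SAP*

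**What the plan says.** Section C1 sets a yes/no outcome: "The primary endpoint will be treatment failure at week 24". Its failure criteria concern lesions, inflammation grade and visual acuity. Stopping drug, withdrawing, or having no week-24 assessment is not among them.

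Section G3 gives the analysis set and its timing together: "Patients will be analyzed by intent to treat when all 5 patients in a treatment arm have either completed 6 months of therapy", or have "discontinued therapy due to study withdrawal or indications for treatment cessation". It states the result as a percentage, "We expect 40-60% of patients to meet the primary endpoint in each arm", and sets this against an external placebo arm, "which had a treatment failure rate of 80% at 24 weeks".

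Section G5 is a single sentence: "Patients with missing outcome data in the primary endpoints will be censored for the initial analysis for efficacy". It does not define censoring, and neither G5 nor any other section describes an analysis after the initial one.

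Four other places bear on who ends up with a missing outcome:
- C2 lists time to treatment failure, but only as exploratory.
- E2 2.f asks patients who withdraw to attend an Early Exit Visit. F4 collects the eye measures at that visit.
- E2 2.h ends study follow-up for patients who withdraw.
- E2 2.i keeps patients who stop drug in the study. Those who have not failed are watched for relapse, and the follow-up is also described as serving safety.

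**The concern.** An intent-to-treat percentage has every enrolled patient in its denominator. If G5 removes patients whose primary outcome is missing, the figure reported is an observed-case rate, and the two sections describe different numbers.

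The patients affected can be foreseen. E2 2.i lets a patient with shingles or an opportunistic infection choose to withdraw. If that patient has not met a failure criterion by the Early Exit Visit, the exit status may be known but the week-24 status will not be. G5 is then the only rule that applies.

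The second issue is narrower. G3 treats a patient as finished when drug is discontinued. A patient who stops without failing and stays in the study can still relapse before week 24. If the others have already finished or stopped, the analysis can run before that patient's status is known, and G5 could then drop the patient as missing. The plan also does not say whether a relapse after stopping drug counts towards the primary endpoint.

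What is at stake is the descriptive failure rate and how it sits beside the plan's only benchmarks, 40-60% and 80%.

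**Working it through.** **Inputs.** Enrolment is at most 5 (G1). The endpoint is binary at week 24 (C1). The benchmarks are 40-60% and 80% (G3). At 5 patients these are 0.4 × 5 = 2 to 0.6 × 5 = 3 failures, and 0.8 × 5 = 4 failures. The plan contains no power or precision figure to reproduce. It gives no missing rate, so the number missing is an assumption.

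**Formulas.** With n enrolled, m missing and f observed failures:
- observed-case rate (the natural reading of G5): f/(n − m)
- missing counted as non-failure: f/n
- missing counted as failure: (f + m)/n
- distance between the two bounds: m/n

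**Results.**

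| n | m | f | Observed-case | Non-failure bound | Failure bound |
|---|---|---|---|---|---|
| 5 | 1 | 1 | 1/4 = 25% | 20% | 40% |
| 5 | 1 | 2 | 2/4 = 50% | 40% | 60% |
| 5 | 1 | 3 | 3/4 = 75% | 60% | 80% |
| 5 | 2 | 1 | 1/3 = 33% | 20% | 60% |
| 5 | 2 | 2 | 2/3 = 67% | 40% | 80% |
| 4 | 1 | 2 | 2/3 = 67% | 50% | 75% |

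Each missing patient separates the bounds by 1/5 = 20 points if 5 enrol, and by 1/4 = 25 points if 4 do.

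**Direction.** The observed-case rate lies below the missing-as-failure rate unless every observed patient failed. It lies above the missing-as-non-failure rate whenever at least one observed patient failed. Exclusion can therefore move the figure either way, depending on what would have happened to the missing patient.

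**If Kaplan-Meier censoring was meant.** For n = 5 with 1 censored, the estimate depends on when censoring falls:
- 2 failures: 1 − (3/4)(2/3) = 50.0% if censored first; 1 − (4/5)(2/3) = 46.7% if between the failures; 1 − (4/5)(3/4) = 40.0% if last.
- 3 failures: 1 − (3/4)(2/3)(1/2) = 75.0% if censored first; 1 − (4/5)(3/4)(2/3) = 60.0% if last.

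The meaning of the word therefore changes the reported figure by up to 10 points in the first case and 15 in the second.

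**How likely is any missing outcome?** If each patient independently has a probability d of a missing outcome, the chance of at least one among 5 is 1 − (1 − d)^5. For assumed d of 5%, 10%, 20% and 30% this is 23%, 41%, 67% and 83%.

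**The case against.** The strongest reply is that little depends on the rate. The plan says "A maximum of 5 patients with uveitis will be enrolled" and "This study is not powered to draw statistical conclusions". There is no test and no decision rule on efficacy, and a listing of five outcomes would show everything. This stands, and it sets the severity. It does not remove the point, because the plan states a percentage and a placebo comparison but promises no such listing.

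A second reply is that censoring may carry its time-to-event meaning, since C1 accumulates failures over visits and C2 lists time to failure. In that case the conflict with intent to treat is softer. That reading is possible, but no time-to-event estimate is planned for the primary endpoint.

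A reader might infer that one patient's handling always decides which benchmark the result resembles. The figures do not support that. With 2 observed failures and 1 missing, all three handlings (40%, 50%, 60%) stay inside the expected range; the result moves between benchmarks only in some cases, such as 3 failures and 1 missing. Chance also blurs the benchmarks at this size. With 5 patients, a true failure rate of 60% gives 4 or more failures with probability 34%, and a true rate of 80% gives 3 or fewer with probability 26%.

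The early-trigger case needs a patient who stops drug without failing, stays in the study, and is short of week 24 when everyone else has finished or stopped. A patient who has already failed has a known status and is unaffected.

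**Conclusion.** The point holds as a minor one. G5 states a rule which, for a binary endpoint reported as a percentage, most naturally yields an observed-case rate where G3 promises intent to treat. The later analysis that the word *initial* implies is nowhere described. Separately, G3's trigger can be met before the week-24 status of a patient still in the study is known.

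The effect is limited to the reported rate and its comparison with 40-60% and 80%. If 5 enrol and 1 outcome is missing, the bounds lie 20 points apart. Only in some configurations does this reach from the expected range to the placebo rate: 3 observed failures give 75% observed-case, with bounds of 60% and 80%. These sizes rest on an assumed number of missing outcomes and on reading censoring as exclusion.

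A reader might conclude that the rule favours tofacitinib. The documents do not establish that. A patient who leaves might or might not have failed by week 24, and exclusion moves the rate down in the first case and up in the second.

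**What to change.** 1. **G5.** Keep all enrolled patients in the denominator. Count as an observed failure any patient documented as meeting a C1 criterion at a study visit, including the Early Exit Visit and visits after drug cessation. For patients whose week-24 status is unknown, report the failure rate twice, with missing counted as failure and as non-failure. Put the observed-case rate beside these, with a patient-level listing that gives the reason for each missing status.
2. **G5.** Delete the word *initial* or define the later analysis. Keep censoring for the exploratory time-to-failure analysis only.
3. **G3.** Run the analysis when every enrolled patient has reached week 24, met the failure definition, or withdrawn from the study. Refer to every enrolled patient and not to all 5, because G1 makes 5 a maximum.

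**Cost.** A few sentences and very little analysis work; F4 already schedules the eye measures, including at the Early Exit Visit. The result becomes a range in place of one figure whenever an outcome is missing, and the rate may look less favourable. The analysis waits longer only if a late-enrolled patient stops drug early without failing and stays in the study. If the last-enrolled patient stops at week s, the extra wait is at most about 24 − s weeks: 20 weeks for a stop at week 4, 4 weeks for a stop at week 20, give or take the 2-week visit window.
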